5.3. Demographics and Baseline Characteristics

Patient demographic and baseline characteristics, including date of birth, age, ethnicity, race, sex, weight, height, body mass index, preventive medication use, time since initial migraine diagnosis, migraine classification (CM or EM), triptans/ergots use during baseline, migraine with aura, and ECG findings, will be examined to assess the comparability of the treatment groups and will be summarized using descriptive statistics. Categories for missing data will be presented if necessary.

The baseline electronic headache diary device efficacy variables will be summarized.

5.4. Medical History

All medical history will be coded using the Medical Dictionary for Regulatory Activities (MedDRA) version 26.0 or higher. The incidence of medical history abnormalities will be summarized using descriptive statistics by system organ class (SOC) and preferred term (PT). Patients are counted only once in each PT and SOC category. Summaries will be presented by treatment group and for all patients.

5.5. **Prior Therapy and Medication**

Any prior therapy, medication, or procedure a patient has had before study drug administration (ie, procedures for the treatment of migraine [eg, nerve blocks]) a patient has had within 6 months before study drug administration and preventive medications taken within 10 years) will be recorded on the CRF. Trade name or international nonproprietary name (INN), indication, and dosage will be recorded. The sponsor will encode all therapy and medication according to the World Health Organization (WHO) drug dictionary (WHODrug) version 2023MAR01DDE or higher.

Details regarding excluded prior medications, including preventive migraine treatments, are described in the exclusion criteria in the study protocol.

The incidence of prior therapies and medications will be listed by double-blind treatment group and summarized using descriptive statistics by therapeutic class and PT. Patients are counted only once in each therapeutic class category, and only once in each PT category. Prior therapies and medications will include all medications taken and therapies administered before the 1st day of study drug administration.

The prior medications will also be summarized for the following categories:

- butalbital for migraine/headache
- ergots for migraine/headache
- non-steroidal anti-inflammatory drugs (NSAIDs) for migraine/headache
- NSAIDs for other reason than migraine/headache
- opioids for migraine/headache
- opioids for reasons other reason than migraine/headache
- preventive medication from protocol Appendix K for migraine/headache
- preventive medication from protocol Appendix K for other reason than migraine/headache
- triptans for migraine/headache

5.6. Childbearing Potential and Methods of Contraception

For female patients, information related to childbearing potential, and menopause will be collected and listed.

For female and male patients, methods of contraception will be collected and listed.

5.7. Study Protocol Violations

Protocol deviations (PD) will be collected and reviewed by the study team prior to database lock and will be provided in a data listing. Patients with at least 1 important PD will be summarized for each category using descriptive statistics.

6. EFFICACY ANALYSIS

6.1. General

For the purposes of this study;

- CM is defined as headache occurring on ≥ 15 days during the screening period.
- EM is defined as headache occurring on <15 days during the screening period.

All e-diary data collected during the screening period, regardless of the duration beyond 28 days (e.g., 30 days), will be included and analyzed. There will be no exclusion of any e-diary data during the screening period.

A migraine day is endorsed when at least one of the following situations occurs:

- A calendar day (0:00 to 23:59) demonstrating at least 2 consecutive hours of a headache meeting the criteria for migraine with or without aura
- A calendar day (0:00 to 23:59) demonstrating at least 2 consecutive hours of a headache meeting the criteria for probable migraine, a migraine subtype where only 1 migraine criterion is missing
- A calendar day (0:00 to 23:59) demonstrating a headache of any duration that was treated with migraine-specific medications (triptans and ergot compounds)

A headache day of at least moderate severity is endorsed when at least 1 of the following situations occurs:

- a calendar day (0:00 to 23:59) demonstrating at least 2 consecutive hours of headache of at least moderate severity
- a calendar day (0:00 to 23:59) demonstrating a headache of any duration that was treated with migraine-specific acute medications (triptans and ergot compounds)

The derivation logic for both migraine day and headache day of at least moderate severity is presented in Appendix B.

In addition, a headache day of any severity is endorsed when at least 1 of the following situations occurs:

- a calendar day (00:00 to 23:59) demonstrating at least 2 consecutive hours of headache of any severity
- a calendar day (0:00 to 23:59) demonstrating a headache of any duration that was treated with migraine-specific acute medications (triptans and ergot compounds)

The endpoint of headache hours of at least moderate severity is obtained directly from the corresponding electronic headache diary device question (Question A5).

The endpoint of days of use of any acute headache medication is obtained directly from the corresponding electronic headache diary device questions (Question C1=Yes or C3=Yes and C2 has a medication present).

The endpoint of days of use of migraine specific acute medications (triptans and ergot compounds) is obtained directly from the electronic headache diary device question where Question C1=Yes and C2=ergot or triptan.

Other efficacy variables (days with nausea or vomiting, days with photophobia and phonophobia) will be derived using the e-diary data collected through the corresponding headache diary questions which can be found in Appendix A.

Patient satisfaction is measured by the PGIC scale which is a validated generic tool for the assessment of overall change in the severity of illness following treatment. Patients will rate how they describe the change (if any) that their migraine/headaches have had in their general quality of life and health status since beginning the treatment in this study on a 7-point scale, where 1=no change (or condition got worse); 2=almost the same, hardly any change at all; 3=a little better but no noticeable change; 4=somewhat better, but the change has not made any real difference; 5=moderately better and a slight but noticeable change; 6=better and a definite improvement that has made a real and worthwhile difference; and 7=a great deal better and a considerable improvement that has made all the difference.

Based on the PGIC assessment, a dichotomous scale of "Yes" or "No" will be derived. A favorable change is score of 5-7 = 'Yes', which means there is significant improvement with the treatment. If the response is 1-4 = 'No', it is considered no significant change.

The *monthly average number of days or hours* of efficacy variables (eg, migraine days, days of headache with at least moderate severity, days of headache with any severity, total hours of headache with at least moderate severity, days of use of any acute headache medications, days with nausea or vomiting, days with photophobia and phonophobia, days of use of migraine-specific acute headache medications (triptans and ergot compounds) *during the 12-week double-blind period* after the 1st dose of study drug and *during the 12-week open-label period* after the 4th dose of study drug will be derived and prorated to 28 days equivalent using the following formula.

 $\frac{\sum Days \text{ of efficacy variable over the 12 week period}}{\sum Days \text{ with assessments recorded in the eDiary for the 12 week period}} \times 28 (1)$

The *monthly number of days or hours* of efficacy variables *during the 4-week double-blind period* after the 1st dose of study drug and *during the 4-week open-label period* after the 4th dose of study drug will be derived and prorated to **28** days equivalent using the following formula.

 $\frac{\sum Days \text{ of efficacy variable during the 4 week period}}{\sum Days \text{ with assessments recorded in the eDiary for the 4 week period}} \times 28 \quad (2)$

Formula (2) will also be used for the variables *during the 4-week period* after each dose for months 1, 2, and 3 used in the sensitivity analysis for the primary estimand.

The *baseline values* will be calculated using all data collected in the run-in period and will be derived and prorated to **28** days equivalent using the following formula.

 $\frac{\sum \text{Days of efficacy variable during the run - in period}}{\sum \text{Days with assessments recorded in the eDiary for the run - in period}} \times 28 (3)$

The *percentage of reduction* in the monthly average number of an efficacy variable will be calculated as

 $\frac{baseline \ value - postbaseline \ value}{baseline \ value} \times 100\%$ (4)

where the baseline value is calculated by formula (3) and the postbaseline value in the equation is calculated by formula (1) for the variables *during the 12-week double-blind period or 12-week open-label period* or by formula (2) for the variables *during the 4-week double-blind period* after 1st dose of study drug *or the 4-week open-label period* after 4th dose of study drug.

For the endpoints relating to a percentage reduction the patient is considered as a responder reaching 50%, 75%, or 100% reduction if the percent reduction in the efficacy variable as calculate by formula (4) is 50% or more, 75% or more, or 100% respectively. If a patient is early discontinued from the study, he/she will be counted as a non-responder.

Summaries will be presented by treatment group in the double-blind period for both the interim analysis at the end of the double-blind period and for the interim analysis at the end of the open-label period. There will be a column for placebo and a column for all fremanezumab-treated patients unless otherwise noted. Descriptive statistics for all efficacy data will be presented by-month over the 12-week period after the 1st dose of study drug for the first interim analysis and presented by-month over the 12-week period after the 4th dose of study drug for the second interim analysis.

The mITT analysis sets will be used for all efficacy analyses unless otherwise noted. As randomized stratification factors will be used for all relevant analyses unless otherwise noted. Summaries will be presented by treatment group as randomized, unless otherwise noted.

6.2. Primary Efficacy Endpoint and Analysis

6.2.1. Primary Estimand

The primary estimand will be the difference in adjusted means between fremanezumab group and placebo group in the population that comprises the patients in the double-blind mITT analysis set for the change from baseline in the monthly average number of migraine days during the 12-week period after the 1st dose of IMP. The intercurrent events (ICEs) that may affect the efficacy endpoint will be handled as per Table 1.

Intercurrent event	Strategy
Patient early terminates from the IMP	Treatment policy ¹
Patient receives the wrong IMP due to medication errors	Treatment policy ¹
Patient receives a rescue medication due to worsening symptoms	Treatment policy ¹

Table 1: Intercurrent Event Strategies: Primary Estimand

¹Treatment policy: if observations are collected after the occurrences of the ICEs, the observations will be included in the calculation of the primary endpoint for the primary analysis.

The baseline values will be derived using formula (3). The post baseline values will be derived using formula (1), and *the change* is calculated as *postbaseline – baseline value*.

6.2.2. Primary Analysis of the Primary Estimand

The hypothesis testing for the primary analysis is:

 $H_o: \delta_1 = \delta_2$ vs $H_a: \delta_1 \neq \delta_2$

where δ_1 and δ_2 are the parameters of mean change from baseline in the monthly average number of migraine days during the 12-week period after the 1st dose of IMP for the combined TEV-48125 treatment groups and the placebo group respectively.

An analysis of covariance (ANCOVA) will be performed, including treatment (combined TEV-48125 groups vs. placebo) and stratification factors (as randomized) of migraine type (CM vs EM) and baseline preventive medication use (yes vs no) as fixed factors, as well as baseline number of migraine days as a covariate in the model. For the individual treatment groups (combined TEV-48125 groups and placebo) the least square (LS) mean, standard error (SE) and corresponding 95% confidence interval will be presented. For the treatment difference (combined TEV-48125 groups - placebo) the LS mean, SE, corresponding 95% confidence interval and p-value for comparison will be presented.

The statistical test will be two-sided at the alpha = 0.05 level of significance. Model fitting assumptions will be investigated.

Example SAS code is provided in Appendix D.

A hierarchical procedure will be used to control the type 1 error rate, as described in Section 7.

6.2.3. Sensitivity Analysis of the Primary Estimand

6.2.3.1. MMRM Analysis

The sensitivity of the primary analysis to missing data will be assessed using mixed-effects model for repeated measures (MMRM) via restricted maximum likelihood estimation and assuming a missing at random (MAR) mechanism.

Each patient's monthly number of migraine days *during the 4-week period* for month 1, month 2 and month 3 will be calculated by formula (2) in Section 6.1 based on the electronic headache diary device responses for that month. If a patient is early terminated or has intermittent missing days (ie. fewer than 10 days of electronic headache diary entries for a month), that month's value will be considered as missing as described in Section 4.3.

The model will include treatment, month and stratification factors of migraine type (CM vs EM) and baseline preventive medication (yes vs no) use as fixed factors and treatment-by-month interaction effects, and baseline number of migraine days as a covariate. Patient will be included in the repeated statement as a random effect. The unstructured covariance model will be used for repeated observations within patients. If the model does not converge, then simpler covariance structures with fewer parameters will be used: heterogeneous autoregressive (1), heterogeneous compound symmetry, autoregressive (1), and compound symmetry, and the

variance covariance structure which minimizes the Akaike's information criterion (AIC) will be selected.

The 12-week monthly average number of migraine days will be estimated by the LS means of the overall treatment effect over 3 months for each treatment group (combined TEV-48125 groups and placebo) along with SE and 95% confidence interval, and the LS means will be calculated for the treatment difference (combined TEV-48125 groups - placebo) along with SE, 95% confidence interval and nominal p-value. These calculations will be done by month as well as for the overall double-blind treatment period.

The LS means \pm SE of monthly change from baseline values estimated by MMRM will be plotted by month for each treatment group.

Example SAS code is provided in Appendix D.

In addition, a further MMRM analysis will also be performed to examine the sensitivity of the statistical inferences against departure from the assumption of time-independent effect of baseline number of migraine days. The model will be the same as that above, but will include a time-by-baseline interaction along with baseline as a continuous covariate. Therefore the model will include the fixed categorical effects of treatment, month, stratification factors of migraine type (CM vs EM) and baseline preventive medication (yes vs no) and treatment-by-month interaction, as well as the continuous, fixed covariates of baseline number of migraine days and baseline number of migraine days-by-month interaction. Example SAS code is provided in Appendix D.

6.2.3.2. Analysis with Multiple Imputation Method

Multiple imputation (MI) method will be applied to impute the monthly missing data assuming a missing not at random (MNAR) mechanism. The data will be processed by the following steps.

- If a patient has <10 days of electronic headache diary device data in a month, that month's value will be considered missing before the MI procedure.
- For the patients in the active treatment groups who are early terminated with reasons of treatment-related adverse event or lack of efficacy, they will be assigned to placebo group so their missing values will be imputed using data from the placebo treated patients.
- Run SAS PROC MI procedure to create 100 complete datasets.
- Within each imputed data set, for a patient who has partial, say X days (X<28), electronic headache diary device data in a month, the monthly value will be replaced by ∑(oberseved migraine days) + (28 X) * imputed value/28
- The monthly average number of migraine days *during the 12-week period* after the 1st dose of study drug will be the average of month 1, month 2, and month 3 values.

Each dataset will be analyzed using the same ANCOVA model as described in Section 6.2.2. The LS means and standard errors from each analysis will be output to a SAS data set. SAS MIANALYZE procedure will be used to generate the final LS means (\pm SE) for the treatment groups and the treatment difference (TEV-48125 - placebo) as well as p-values associated with

treatment differences. The 95% confidence intervals for the treatment difference will also be constructed.

The output dataset will contain the estimate of the mean difference and the standard error of the estimate from each of the 100 datasets. SAS procedure, PROC MIANALYZE, will be used to generate an overall p-value and 95% CI for the treatment difference.

This sensitivity analysis will be performed on the ITT analysis set.

Example SAS code is provided in Appendix D.

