If a patient is withdrawn from the study or discontinues IMP for multiple reasons that also include adverse events, the relevant page of the CRF should indicate that the withdrawal/discontinuation was related to an adverse event. An exception to this requirement will be the occurrence of an adverse event that, in the opinion of the investigator, is not severe enough to warrant discontinuation but that requires the use of a prohibited medication, thereby requiring discontinuation of the patient. In such a case, the reason for discontinuation would be “Other,” specifying the details as “need to take a prohibited medication,” not the adverse event.

In the case of patients lost to follow-up, attempts to contact the patient must be made and documented in the patient’s medical records.

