3.2. Modified Intent-to-Treat Analysis Sets

The double-blind modified intent-to-treat (mITT) analysis set is a subset of the ITT analysis set including only patients who receive at least 1 dose of IMP and have at least 10 days of post baseline efficacy assessment on the primary endpoint. The double-blind mITT analysis set will be used for the primary estimand analysis and all of its sensitivity analyses. The open-label mITT analysis set is a subset of the ITT analysis set including only patients who receive at least 1 dose of IMP during the open-label treatment period and have at least 10 days of post baseline diary entries during the open-label treatment period.

In the mITT analysis sets, treatment will be assigned based on the treatment to which patients were randomized, regardless of which treatment they actually received.

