14. CHANGES TO ANALYSES SPECIFIED IN THE STUDY PROTOCOL

The following endpoint has been removed in the SAP due to the necessary data not being collected:

• mean change from baseline in the monthly average number of days with most bothersome symptoms during the 12-week period after the 1st dose of IMP

The wording of the following endpoint has been changed as shown.

Wording from protocol:

• mean change from baseline (day 0) of patient satisfaction, as measured by the PGIC scale, at 4 weeks after the last (6th) dose of study drug

New wording in SAP:

• assessment of patient satisfaction, as measured by the Patient Global Impression of Change (PGIC) scale, at visit 8

A multiple imputation analysis has been added in Section 6.2.3.2 as an additional sensitivity analysis of the primary estimand to assess the sensitivity of the primary analysis to missing data assuming the data is missing not at random.

The definitions for CM and EM have been modified; CM is defined as having ≥ 15 headache days during the baseline period whilst < 15 headache days during the baseline period is classed as EM.

The following analysis has been removed in the SAP due to minimal COVID-19 diagnoses occurring:

• Missing data or visits due to the COVID-19 pandemic will be evaluated for the primary and secondary endpoints. COVID-19 may have an impact on patients' migraine symptoms, with headache reported to be a common complication as a result of contracting the disease. All COVID-19 cases will be included in the primary analysis; however, observations following COVID-19 diagnosis will be discarded from the calculation of the monthly average endpoint. The data handling strategy will be detailed in the statistical analysis plan.

The following subgroup analysis has been removed in the SAP due to disease severity being collected daily rather than just once during the baseline period:

• Patients by disease severity (Mild, Moderate, Severe)

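### The only MNAR-labelled analysis of the primary endpoint uses placebo-based imputation for two stop reasons only, leaves never-dosed fremanezumab patients on drug-arm imputation, and names an analysis set that SAP 3.2 contradicts

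*SAP*

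**What the plan says.** SAP 6.2.3.2 sets out a multiple imputation analysis to "impute the monthly missing data assuming a missing not at random (MNAR) mechanism". SAP 14 lists it as an addition to the protocol, intended to "assess the sensitivity of the primary analysis to missing data assuming the data is missing not at random".

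The only departure from MAR is the treatment label used for imputation. Active-arm patients who are "early terminated with reasons of treatment-related adverse event or lack of efficacy, they will be assigned to placebo group". Appendix D imputes months 1 to 3 from that label (TRTMI), the two stratification factors, baseline and earlier months. It then analyses the completed data by randomised arm. In partly observed months the observed days are kept.

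On the population, SAP 6.2.3.2 ends: "This sensitivity analysis will be performed on the ITT analysis set". SAP 3.2 says: "The double-blind mITT analysis set will be used for the primary estimand analysis and all of its sensitivity analyses". SAP 6.2.3.2 sits under the heading for sensitivity analyses of the primary estimand, so both statements apply to it. SAP 3.1 defines ITT as everyone randomised. SAP 3.2 limits double-blind mITT to patients with at least one dose and at least 10 days of post-baseline assessment.

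The primary estimand (SAP 6.2.1) handles early termination of IMP by treatment policy.

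**The concern.** An MNAR analysis is there to show whether the result survives if unobserved patients did worse than the observed data predict. Here that assumption is applied to two stop reasons. Fremanezumab patients who withdraw consent, are lost to follow-up or stop for an unrelated adverse event keep the fremanezumab label. Protocol 4.3 adds a further route out of the rule. An adverse event that is not itself severe enough to stop treatment but "requires the use of a prohibited medication, thereby requiring discontinuation of the patient" is recorded under the reason Other.

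The clearest problem is the never-dosed patient. In the ITT set, someone randomised to fremanezumab and never injected cannot plausibly carry either qualifying reason, so all three months are drawn from the drug arm. Under treatment policy that credits a drug response to a patient who had no drug, which favours fremanezumab. SAP 4.4 counts study days from the first dose, so months 1 to 3 are not defined for such a patient either.

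The conflict over the analysis set decides whether never-dosed patients, and those with under 10 diary days, enter the analysis at all.

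**Working it through.** **1. Does another planned analysis fill the gap?**

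- MMRM (6.2.3.1): stated as "assuming a missing at random (MAR) mechanism". Its variant only adds a baseline-by-month term.
- 6.2.3.3 changes the strata to actual values; 6.2.3.4 splits the regimens.
- First and second supplementary estimands (6.2.4): removed values are replaced by averages from the same treatment group.
- Third and fourth supplementary estimands: same method in the ITT or per-protocol set.

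The visible text has no delta-adjusted, tipping-point or all-reason reference-based analysis.

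**2. The plan's own figure.** Inputs: 163 completers per group, at least 90% power, 12% discontinuation and 372 randomised (SAP 2.4), with a two-sided 0.05 test (SAP 6.2.2). The effect of 1.6 days and SD of 4.45 days are visible only in the Amendment 01 log (Protocol 16.4); the current section 9.1 has a redacted block.

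- n = 2 × (1.960 + 1.282)² × (4.45/1.6)² = 162.6, so 163 per group
- 163/0.88 = 185.2, so 186 per arm and 372 in total

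Both figures reproduce, which supports using 1.6 and 4.45 below.

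**3. Size of the shift.** Let d = 0.12, let s be the share of fremanezumab dropouts with the two reasons, and let m be the share of the 12 weeks missing. The documents give neither s nor m.

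- Patients: 0.12 × 186 = 22.3. At s = 1/3, about 7 are placebo-imputed and about 15 are not.
- Shift under the written rule = 1.6 × d × s × m. At s = 1/3, m = 0.5: 1.6 × 0.12 × 0.333 × 0.5 = 0.032 day. At s = 0.2 it is 0.019 and at s = 0.5 it is 0.048.
- Shift if all dropouts are placebo-imputed = 1.6 × d × m = 1.6 × 0.12 × 0.5 = 0.096 day.
- Gap at s = 1/3, m = 0.5: 0.096 − 0.032 = 0.064 day.

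Gap in days, 1.6 × 0.12 × m × (1 − s), over a wider range:

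| m | s = 0 | s = 0.25 | s = 0.50 | s = 0.75 | s = 1 |
|---|---|---|---|---|---|
| 1/3 | 0.064 | 0.048 | 0.032 | 0.016 | 0 |
| 2/3 | 0.128 | 0.096 | 0.064 | 0.032 | 0 |
| 1 | 0.192 | 0.144 | 0.096 | 0.048 | 0 |

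The formula is an approximation. It gives each drug-arm imputed month the full average difference and each placebo-imputed month none. The actual model also uses the patient's own baseline and earlier months.

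**4. Never-dosed patients.** With all three months imputed, each adds 1.6/186 = 0.0086 day.

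**5. Against the precision of the trial.** SE = 4.45 × √(2/186) = 0.461 day, ignoring covariate adjustment and imputation variance. The 0.064-day gap is 0.14 SE. The ratio of effect to SE is (1.6 − 0.032)/0.461 = 3.40 under the written rule and (1.6 − 0.096)/0.461 = 3.26 with all dropouts placebo-imputed.

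**The case against.** Reason-based placebo imputation is a legitimate prespecified MNAR departure, and several points count against a stronger criticism.

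- A reader might infer that other dropouts are imputed as if still on drug with full benefit. The documents do not support that. The model conditions on the patient's own baseline and earlier months, so poor early months predict poor later ones. The drug-arm data can also include observations after IMP was stopped, which Protocol 3.1 encourages sites to collect.
- A reader might infer that most dropouts escape the rule. The documents give no split of stop reasons.
- A reader might infer that the analysis simply repeats the primary one. It does not: the primary ANCOVA prorates each patient's observed days and has no imputation model.
- Quarterly patients receive all their double-blind active drug at visit 2. Stopping later means missing placebo injections only, and SAP Table 2 sets aside post-stop data only for the monthly regimen. Placebo imputation for every early stop is therefore deliberately conservative for half the pooled arm.
- The 12% is anticipated non-completion of a study that includes open-label and follow-up periods. It is not stated as missing data in weeks 1 to 12.
- Randomisation and first dose both fall at visit 2, so never-dosed patients should be few.
- The general rule in Protocol 4.3 records withdrawals for several reasons that include an adverse event as adverse-event related. The Other category is a narrow exception.
- SAP 6.1 allows departures from mITT where noted, and 6.2.3.2 names ITT explicitly, so the intention is probably ITT.

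All of this limits the size and argues against discarding the reason-based rule. It does not justify drug-arm imputation for a patient never dosed, it does not supply a broader departure from MAR, and SAP 3.2 still carries no exception.

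**Conclusion.** The point holds in a limited form. The one analysis labelled MNAR applies a non-MAR assumption to a subset of fremanezumab dropouts of unknown size and may depart little from MAR. It credits never-dosed fremanezumab patients with a drug-arm response, and its population is stated in two incompatible ways.

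The effect is modest: about 0.03 day under the written rule against about 0.10 day with all dropouts placebo-imputed, and about 0.009 day per never-dosed patient. These figures rest on 12% dropout falling wholly in the double-blind period, half of the 12 weeks missing, one third of dropouts with the two reasons, and the 1.6-day effect seen only in the amendment log. Over the full grid the gap runs from 0 to 0.19 day.

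A reader might go further and infer that the primary conclusion is at risk. The numbers do not support that: the gap is about 0.14 SE under the central assumptions. What is weakened is the reassurance that this sensitivity analysis can give.

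**What to change.** - **SAP 6.2.3.2 and Appendix D:** set TRTMI to placebo for every patient randomised to fremanezumab who was never dosed.
- **SAP 4.4:** define months 1 to 3 for never-dosed patients, for instance as 28-day windows from randomisation. The present rule for missed doses covers later doses only.
- **SAP 6.2.3.2:** keep the reason-based run and add a second run with TRTMI set to placebo for every fremanezumab patient who stops IMP early for any reason and has missing months. Keep observed post-stop data as observed. State that this run is deliberately conservative for dosed quarterly patients.
- **SAP 3.2:** after the sentence on sensitivity analyses, add the exception that 6.2.3.2 uses ITT.

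The cost is SAP wording, one derived variable and one extra run of existing code. The sensitivity estimate will be slightly less favourable to fremanezumab. The changes should be settled before the unblinding at the first interim lock.
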